4. PLANNED ANALYSES

The following analyses will be performed for this study:

- Analyses for the DMC meetings.

- Primary data analysis.
- Final data analysis.

4.1. DMC MEETINGS

There were two planned timepoints for DMC meetings to review the safety and tolerability data:

- DMC 1: After the first 30 enrolled subjects completed the Week 4 visit or terminated early from the study, whichever occurs first.
- DMC 2: After all subjects completed the Week 4 visit or terminated early from the study, whichever occurs first.

These two DMC analyses have been described in a separate SAP which was authorized prior to each of the DMC analyses. Refer to the DMC SAP for further details.

4.2. PRIMARY DATA ANALYSIS

The trigger for the planned primary data analysis is when all subjects have completed the Week 28 visit (that is when all subjects have completed the last visit during the treatment stage at Week 24 or early terminated from the study or treatment, whichever occurs first, plus 4 weeks post-treatment follow-up). All planned analyses described in this SAP, except for analysis for visits after Week 28 (which will be analyzed as part of the Final Analysis, see Section 4.3), will be performed by [REDACTED] Biostatistics following:

- Sponsor authorization of this SAP.
- Sponsor authorization of the analysis sets as relevant (refer to Section 5 for details).
- The relevant data cut-off being reached and the database lock for primary data analysis (refer to the latest version of the Interim Database Lock Plan for specific details).
 - No data collected or protocol deviations recorded after the cut-off date will be included in the analysis.
- Study unblinding (refer to the latest version of the unblinding plan for specific details around blinding).
 - Project teams will be unblinded, subjects to remain blinded until end of study.

4.3. FINAL DATA ANALYSIS

The trigger for the planned final data analysis is when all subjects have completed the Week 48 visit or early

terminated from the study, whichever occurs first.

All planned analyses relevant to the final data analysis identified in this SAP will be performed by [REDACTED] Biostatistics following final database lock. The final analyses will include:

- Disposition
- Concomitant medications during the Post-Treatment period
- CS7DA4S score by Post-Treatment visit
- 7-day average score of each of 4 CS cardinal symptoms by Post-Treatment visit
- SNOT-22 by Post-Treatment visit
- SF-36 by Post-Treatment visit
- Adverse events (AEs) during the Post-Treatment period
- Vital Signs by Post-Treatment visit
- Physical examination by Post-Treatment visit
- Ophthalmology assessments by Post-Treatment visit

Analysis Sets will be defined as per the primary data analysis.

5. ANALYSIS SETS

Agreement and authorization of subjects included/excluded from each analysis set will be conducted prior to the unblinding of the study (Section 4.2).

5.1. PROCESS FOR ANALYSIS SET ASSIGNMENT

- Preliminary analysis set assignments to each of the analysis sets will be prepared and shared with the sponsor based on an “as clean as possible” data transfer from data management prior to the interim database lock for the primary data analysis.
 - An “as clean as possible” transfer refers to a data transfer where at most there can be limited list of known open queries on the data.
- This preliminary analysis set assignments will be used in the discussions and decisions during the blind data review.

- During the blind data review the impact of those open queries on the data should be assessed with regards to the influence it might have on the analysis set assignments.
- Based on the discussion and decisions made during the blind data review, the final “blinded” analysis set assignments for each analysis set (excluding the PK analysis set, refer to Section 5.7) will be prepared and authorized prior to the interim database lock.
 - “Blinded” analysis set assignment refers to the fact that there are a few reasons that might lead to exclusion from various analysis sets which cannot be assessed in a blinded manner. For example, randomized arm assignment differing to actual arm assignment is a major protocol deviation and will lead to exclusion from the per-protocol analysis set which can only be determined after lock.
 - The outcome of the blind data review will be documented in a Blind Data Review Report and an Excel file indicating the analysis set assignment for all subjects.
- Following primary analysis interim database lock and study unblinding, the various reasons leading to exclusion from analysis sets based on unblinded data will be assessed. The final analysis set assignments will be prepared and shared with the sponsor for final authorization and use in the primary and final data analyses.

5.2. ALL SUBJECTS CONSENTED ANALYSIS SET [CONS]

The all subjects consented (CONS) analysis set will include all subjects who provide informed consent for this study.

Subjects will be included in CONS based on the availability of a date of informed consent, as recorded on the Demography electronic case report form (eCRF).

5.3. ALL SUBJECTS RANDOMIZED ANALYSIS SET [RND]

The all subjects randomized (RND) analysis set will include all subjects in the CONS set who are randomized to study treatment regardless of whether the subject receives study treatment. For analyses and displays based on RND, subjects will be classified according to randomized treatment.

Subjects will be included in RND based on the availability of a randomization date, as recorded on the Randomization eCRF.

5.4. SAFETY ANALYSIS SET [SAF]

The safety (SAF) analysis set will contain all subjects who receive the study treatment (Sham procedure or a dose of

LYR-210) or have a treatment attempt on Day 1. Subjects will be analyzed according to the treatment actually received or attempted. This is the primary analysis set for safety analyses.

Subjects will be included in SAF based on the availability of a procedure date regardless of whether the bilateral insertion procedure was successful, as recorded on the Procedure eCRF page.

5.5. INTENTION-TO-TREAT ANALYSIS SET [ITT]

The Intention-To-Treat (ITT) analysis set will include all randomized subjects who receive the study treatment (Sham procedure or a dose of LYR-210) or have a treatment attempt on Day 1 and have post-Day 1 assessments available. This is the primary analysis set for assessment of efficacy. Subjects will be analyzed according to the treatment they were assigned to at randomization.

For post-Day 1 assessments availability, the following assessments will be considered: MRI (vendor data), UPSIT (UPSIT eCRF), endoscopy (Endoscopy eCRF), a single cardinal CS symptom (electronic patient reported outcomes [ePRO]), or the ePRO questionnaires of SNOT-22 or SF-36v2.

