#### **6.2.3 Study Product Administration**

LYR-210 is designed to be administered intranasally under endoscopy visualization. Subjects who are assigned to either dose of LYR-210 will have LYR-210 administered bilaterally into the middle meatus. Subjects who are assigned to the sham procedure arm, will undergo bilateral mock administration (i.e., sham procedure), consisting of a bilateral insertion of an applicator

(without LYR-210 loaded) into the middle meatus until the applicator tip touches the ethmoid bulla for a minimum of 20 seconds, followed by withdrawal of the applicator. To maintain subject blinding to the treatment assignment, each subject will wear an eye mask (i.e., blindfold) at the time of the LYR-210 administration/sham procedure. An independent, unblinded case manager may be present during day 1 visit to assist product administration.

Following administration procedure, all enrolled subjects will rest for at least 1 hour and be monitored to ensure there is no epistaxis that requires medical attention.

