#### **6.2.4 Enrollment Failure**

The Investigator will be allowed up to two attempts at LYR-210 administration or at the sham procedure per side. A treatment attempt is defined as that an applicator of a LYR-210 or sham article is inserted to a subject's left or right nostril for an attempt of investigational product administration. If the Investigator is unable to administer LYR-210 bilaterally or perform sham procedure successfully into both middle meatuses of a subject, the Investigator will remove any LYR-210 already administered and treat the subject with any appropriate therapy, if necessary. The subject will be considered as an **Enrollment Failure** as described in Section 6.1. Subjects will be followed within 7 ( $\pm$  2) days via telephone for AE and concomitant medication assessment.

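### The set called ITT will usually lose randomized subjects with failed placement, and no planned efficacy analysis brings them back

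*SAP*

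**What the plan says.** SAP 5.5 puts into ITT the randomized subjects who receive treatment or "have a treatment attempt on Day 1 and have post-Day 1 assessments available". The assessments that count are MRI, UPSIT, endoscopy, SNOT-22, SF-36v2, or a diary entry for one cardinal symptom. Membership is by randomized arm.

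Protocol 6.2.4 covers failed placement in either kind of arm: "The Investigator will be allowed up to two attempts at LYR-210 administration or at the sham procedure per side". If bilateral placement does not succeed, "the Investigator will remove any LYR-210 already administered and treat the subject with any appropriate therapy, if necessary". The subject becomes an Enrollment Failure, and the only follow-up written is contact within 7 (± 2) "days via telephone for AE and concomitant medication assessment". In Protocol 8.1, the daily diary is asked of enrolled subjects, and Table 1 is headed as applying to subjects randomized and enrolled.

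In the sham procedure (Protocol 6.2.3) an empty applicator is held against the ethmoid "bulla for a minimum of 20 seconds, followed by withdrawal of the applicator". No depot is deployed.

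The primary analysis (SAP 15.1.2 and 15.1.3) uses ITT subjects with observed baseline and Week 4 scores. Protocol 10.6.1 and 10.6.1.1 run LOCF and multiple imputation on the ITT set, and SAP 15.1.4 names no wider set. SAP 5.3 defines RND, the subjects "who are randomized to study treatment regardless of whether the subject receives study treatment", but no efficacy section refers to it.

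**The concern.** Whether placement succeeds is known only after randomization, and it is judged by site staff who by then know whether the assignment is LYR-210 or sham (Protocol 6.3). If failed placements leave the analysis set, the comparison is no longer between the groups as randomized. Imputation within ITT cannot repair this, because the subjects are not in the set being imputed.

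The loss need not be equal across arms. Deploying a depot on both sides is a more demanding act than touching the bulla with an empty applicator, so more failures under LYR-210 are plausible, though the documents do not say so. At stake is whether any planned efficacy estimate describes all subjects as randomized. At present none does.

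**Working it through.** **1. Do failed placements reach ITT?** The definition admits an attempt, so the deciding condition is the post-Day 1 assessment. The telephone contact of Protocol 6.2.4 collects none of the qualifying items, and the diary and visit schedule are written for enrolled subjects. A stray diary entry or an unscheduled visit could qualify someone, but nothing in the schedule produces one. Subjects randomized but never attempted are outside ITT in any case.

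**2. Would a stray entry help?** Hardly. A CS7DA4S score needs at least 5 of 7 daily totals (SAP 15.1.1). A subject with one entry has no Week 4 score for the primary analysis and no earlier post-baseline score for LOCF to carry. The multiple imputation of SAP 15.1.4 assumes missing at random, fits the first step separately by arm, and has treatment group in the second-step regressions. It would fill in an unplaced LYR-210 subject as if a depot were in position.

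**3. The plan's own power figure.** Inputs from SAP 7.1 are mean changes of -1.30 (sham) and -3.00 (LYR-210), a difference of 1.70, SD 2.4, 21 evaluable per arm and one-sided alpha 0.05.

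Noncentrality = 1.70 / (2.4 × √(2/21)) = 2.30. The noncentral t gives 72.95% with 40 df and 73.4% with 60 df, so the stated 73% is reproduced.

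**4. Size if failures respond like sham.** The allowance of 6 to 9 extra subjects gives 69 to 72 in total. At 69 that is 23 per arm. With k failures in one LYR-210 arm, none in sham, and a mean change of -1.30 in the failures, the all-randomized difference is 1.70 × (23 − k)/23:

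| k | Difference | Reduction |
|---|---|---|
| 1 | 1.63 | 0.07 (4%) |
| 2 | 1.55 | 0.15 (9%) |
| 3 | 1.48 | 0.22 (13%) |

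**5. Dependence on how failures respond.** With failure share f and mean change m in failures, the difference is (1 − f) × 1.70 + f × (−1.30 − m). The failure rate is an assumption. At f = 10%:

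| m | All-randomized difference | Overstatement when failures are left out |
|---|---|---|
| 0 | 1.40 | 0.30 |
| −1.30 | 1.53 | 0.17 |
| −3.00 | 1.70 | 0 |
| −4.00 | 1.80 | −0.10 |

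**6. If the drug has no effect.** Suppose failures are left out of one arm only and differ in prognosis from the other subjects by g points (positive means worse). The shift toward LYR-210 is then f × g. At f = 5% and 10%, one-sided type I error is 5.7% and 6.5% for g = 1, and 4.4% and 3.8% for g = −1. With g = 0 it stays at 5.0%.

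**7. Is baseline available for all randomized subjects?** Not always. Eligibility needs 5 entries in the 7 days before Day 1, without Day 1 (Protocol 8.3.1.1). The SAP baseline covers Day −6 to Day 1 (SAP 6.3). A subject with entries only on Days −7 to −3 has five for eligibility but four in the SAP window, below the minimum of five.

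**The case against.** The strongest reply is that the definition does not exclude failed placement. It names treatment attempts, and one symptom entry is enough, from subjects who have kept the diary for at least a week before Day 1. That is correct. A reader might infer an exclusion by rule; the documents show only a usual consequence of Protocol 6.2.4 combined with the post-Day 1 condition.

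Second, a reader might infer that the estimates do favour LYR-210. The documents do not support that. No failure rate is given for any arm, and the two-attempt rule foresees sham failures too. Protocol 5.4 (criteria 5a and 6b) screens out obstruction and anatomy that would hinder placement, so failures may be few. Other treatment after a failure is allowed, which can cancel or reverse the effect (step 5). Under the null, a prognostic difference is needed (step 6). The figures in step 4 measure dilution under assumed inputs; they do not demonstrate bias.

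Third, SAP 9 already summarizes attempts and reasons for exclusion from each set by randomized arm, and SAP 3.3 moves disposition to the consented set because ITT is incomplete. Those summaries give counts, not an effect estimate.

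Fourth, the study is exploratory with nominal p-values (SAP 7.8). That lowers the priority of the point. It does not supply the missing estimate.

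**Conclusion.** The point holds in a limited form. Randomized subjects with failed placement will usually be absent from ITT and from the LOCF and multiple-imputation analyses, and no planned efficacy analysis uses all randomized subjects.

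The estimates may favour LYR-210 if failures are more frequent in its arms and respond no better than sham. With a sham-like response, the size is about 0.07 points per failure in an arm of 23 (1.70/23). The failure count and the response are assumptions; neither is in the documents. This is an inexpensive improvement and not a flaw that invalidates the primary analysis.

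A reader might also infer that rerunning the existing imputation on RND would settle the matter. It would not: under SAP 15.1.4 the unplaced LYR-210 subjects would be imputed as if treated (step 2).

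**What to change.** - Add to SAP 15.1.4 a Week 4 sensitivity analysis on RND by randomized arm, with failed placements imputed from the sham distribution. Use any diary data these subjects did provide.
- Specify the control-based imputation model. SAP 3.3 announces one, but SAP 15.1.4 describes a missing-at-random model with treatment group. The two sections must be reconciled.
- Where the SAP-window baseline is missing, use the eligibility-window baseline or impute it, and state which.
- Show Enrollment Failure as an explicit line by randomized arm in the SAP 9 disposition and exclusion summaries. If there are none, that line closes the question of failed placements.

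Cost: modest extra programming, since the control-based model is not yet specified, and a sensitivity estimate that may be less favourable. No new data are needed and the primary analysis is unchanged.

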5.6. PER PROTOCOL ANALYSIS SET [PPAS]

The per-protocol analysis set (PPAS) will contain all randomized subjects who received the study treatment, have post-Day 1 assessments as specified in Section 5.5, and are without major protocol deviations at the time of the primary analysis. A major protocol deviation is defined as any protocol deviation potentially affecting the evaluation of the primary and key secondary efficacy endpoints. It is to be noted that a protocol deviation classified as major by the Biostatistical team (resulting in the exclusion of a subject from the PPAS) might be classified as critical, major or even minor by the Clinical team as the Clinical and Biostatistical teams are using different criteria. Please refer to the Protocol Deviations Management Plan for the criteria used by the Clinical team to classify each protocol deviation as critical, major or minor.

This analysis set will be used to perform supportive analysis for the primary, key secondary, and other secondary efficacy including CS7DA4S, 7-day average score of individual symptoms, SNOT-22, and MRI analyses. Major protocol deviations and other reasons for exclusion from the PP analysis set will be identified and finalized by [REDACTED] Biostatistics based on blinded review of the data, prior to the data extraction for the primary analysis and unblinding of the treatment code.

Major protocol deviations and other reasons for excluding subjects from the PPAS include:

- Insufficient essential efficacy data
 - The primary efficacy variable is the change from baseline (CFBL) in the CS7DA4S score at Week 4. The

CFBL for this score will be derived in the ePRO data at the Week 4 timepoint. The subject must have a non-missing CFBL value for CS7DA4S at Week 4.

- Non-eligibility with the protocol specified inclusion/exclusion criteria
 - The subject must have a composite score of CS7DA4S ≥ 7 at Day 1, as derived by ██████████ Biostatistics. A minimum of five daily entries are required for composite score calculation over the seven days leading up to and including Day 1 for assessing the subject's eligibility for participating in the study.
- Use of prohibited rescue medications prior to Week 4 visit, as identified in a regular Medical Data Review and recorded in the Clinical Trial Management System (CTMS) log for protocol deviations. Such medications include:
 - Oral antihistamine, excluding perennial allergic rhinitis patients who have been on a stable dose of antihistamine since screening
 - Nasal decongestants
 - Intranasal corticosteroid sprays
- Insufficient exposure to the study treatment
 - The subject must have been exposed to the treatment for at least 16 weeks. Exposure will be derived as described in Section 13.1.
- Actual and planned treatments are not the same
 - This will be identified at study unblinding, at the time of the primary analysis, by comparing the subject's allocated treatment arm to the kit type of the kit administered to the subject. The randomization data provided by the randomization vendor will be used.
- Pregnancy: Pregnant subjects are not allowed to participate in the study. Pregnancy results are recorded on the Urine Pregnancy Test, and Serum Pregnancy Test eCRFs.

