### **10.1 Analysis Populations**

The following analysis sets are defined for analysis purposes:

- Safety (SAF) analysis set: The SAF analysis set will consist of all randomized subjects who received the study treatment (Sham procedure or a dose of LYR-210) or treatment attempt on Day 1. Subjects will be analyzed according to the treatment actually received or attempted. This is the primary analysis set for safety analyses.
- Intention-to-treat (ITT) set: The ITT analysis will consist of all randomized subjects who received the study treatment (Sham procedure or a dose of LYR-210) or treatment attempt and have post-Day 1 assessments available. Subjects will be analyzed according to the treatment they were assigned to at randomization. This is the primary analysis set for efficacy analyses.
- Per-Protocol (PP) analysis set: The PP analysis set will include all randomized subjects who received the study treatment, have specific post-Day 1 assessments (i.e., non-missing data for the assessment being analyzed), and are without major protocol deviations at the time of the primary analysis. This is a secondary analysis set for the primary, key secondary, and remaining secondary efficacy analyses. Major protocol deviations and the definition of the PP analysis set will be identified and finalized based on blinded review of the data, prior to the data extraction for the primary analysis and unblinding of the treatment code.
- Pharmacokinetic (PK) analysis set: The PK analysis set will include all SAF subjects with at least one evaluable drug concentration post-Day 1. Subjects will be analyzed according to the successful bilateral treatment received (“actual treatment”). As concentration data is required to assign the PK analysis set, this can only be done at study unblinding, at the time of the primary analysis.

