##### **10.6.2.1 CFBL in CS7DA4S at Week 24**

The first key secondary efficacy endpoint is CFBL in CS7DA4S at Week 24. The primary analysis population for this key secondary efficacy endpoint analysis is ITT subjects with available CS7DA4S data at Baseline and Week 24 visit. At each of these visits, a subject is considered as

having an available (NON-missing) CS7DA4S score if the daily ePRO score is available for at least 5 of the preceding 7 days prior to the time point.

The analysis will be carried out using an ANCOVA model for change from baseline in CS7DA4S score at Week 24 which includes terms for the baseline CS7DA4S score as a covariate, and fixed effects for treatment group and the randomization stratification variables, presence of nasal allergy and presence of nasal polyps.

Additional analyses will be performed for the first key secondary endpoint of CFBL in CS7DA4S at Week 24, using this ANCOVA model for the following:

- Subjects in the PP analysis set with available Baseline and Week 24 CS7DA4S score.
- All subjects in the ITT analysis set. Missing Week 24 CS7DA4S data will be imputed by LOCF and by multiple imputation (details of imputation of missing data are discussed in Section 10.6.1.1).
- Assessment of homogeneity across study regions, across nasal allergy groups and across polyp groups will be performed in the same manner as for the primary endpoint as described in Section 10.6.1.2.

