### **11.6 Protocol Deviations**

The Investigator agrees to conduct the study according to the Clinical Protocol and agrees that all persons delegated to perform study procedures will do so as well. An Investigator is not permitted to deviate from the Protocol without the prior written approval of the Sponsor unless there are concerns of subject's safety. Under emergency circumstances, deviations from the Protocol to protect the rights, safety, and well-being of human subjects may proceed without prior approval of the Sponsor and the EC. Such deviations shall be documented and reported to the Sponsor and the EC (as required) as soon as possible.

A protocol deviation is a failure to comply with the requirements specified within this clinical study protocol. Examples of protocol deviations may include enrollment of a study subject who does not meet all of the inclusion/exclusion criteria specified in the protocol, visits performed outside of the protocol specified visit window, and missed study visits. Each site Investigator shall conduct this clinical study in accordance with this clinical study protocol, local regulatory authority regulations, GCP, and any conditions of approval imposed by their ECs.

The Investigator agrees to inform the EC of all protocol deviations according to Institutional requirements. The occurrence of protocol deviations will be monitored by the Sponsor personnel or designee on an ongoing basis. Deviations from the protocol include, but are not limited to, the use of prohibited medications or therapies and out of window visits. All protocol deviations should be documented and explained. Major protocol violations are defined as those that could impact the performance evaluation such as a subject is ineligible, missing key data, received an unauthorized treatment, etc. All subjects with protocol deviations will continue to be followed for safety and performance assessments.

If an Investigator is found to be repeatedly non-compliant with the Clinical Trial Research Agreement, study Protocol or any other conditions of the Clinical Study, the Sponsor at its sole discretion, will either undertake remedial measures to secure compliance or terminate the Investigator's participation in the study.

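### SAP 5.6 makes a Week 4 diary score a condition for every per-protocol analysis, where protocol 10.1 asks only for data on the assessment being analysed, and SAP 3.3 does not declare the change

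*SAP*

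**What the plan says.** Protocol 10.1 says that per-protocol subjects must have received treatment, be free of major deviations, and "have specific post-Day 1 assessments (i.e., non-missing data for the assessment being analyzed". On the use of the set it says: "This is a secondary analysis set for the primary, key secondary, and remaining secondary efficacy analyses". Protocol 10.6.2.1 describes the Week 24 per-protocol analysis as "Subjects in the PP analysis set with available Baseline and Week 24 CS7DA4S score". It mentions no Week 4 score. Protocol 10.6.2.2 repeats the MRI responder analysis in the per-protocol set, again without a Week 4 diary condition.

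SAP 5.6 defines one set, the PPAS. Its opening sentence asks for randomized, treated subjects who "have post-Day 1 assessments as specified in Section 5.5, and are without major protocol deviations at the time of the primary analysis". The list of exclusion reasons that follows begins with insufficient essential efficacy data and states: "The subject must have a non-missing CFBL value for CS7DA4S at Week 4". The scope is wide: "This analysis set will be used to perform supportive analysis for the primary, key secondary, and other secondary efficacy including CS7DA4S", and the sentence goes on to individual symptoms, SNOT-22 and MRI. SAP 15.2.4.1, 15.2.4.2 and 15.2.4.5 repeat the CS7DA4S and individual-symptom, Zinreich and SNOT-22 analyses in this set. No endpoint-specific exception is given.

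SAP 3.3 lists the changes from the protocol, including a redefined safety set and a different set for disposition. The Week 4 condition is not among them.

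**The concern.** The protocol ties the data condition to each endpoint. The SAP ties it to one endpoint and carries it to all the others. A Week 4 score exists only if at least 5 of the 7 daily totals in Days 23-29 are available, and a daily total exists only if all four symptoms were scored (SAP 6.6.1, Table 2, and 15.1.1). Three missed or incomplete mornings in that week are enough to remove a subject from every per-protocol result. That includes the Week 24 MRI analysis, whose scores come from an imaging vendor and do not use the diary.

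A per-protocol analysis of Week 24 should describe adherent subjects who can be evaluated at Week 24. Under SAP 5.6 it also depends on diary completeness 20 weeks earlier. Precision is lost, the set no longer matches the protocol's definition, and a reader who relies on SAP 3.3 would not know.

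**Working it through.** **1. Compare the texts for one subject.** Take a subject with 4 of 7 complete daily scores in Days 23-29, valid Week 24 diary and MRI data, at least 16 weeks of exposure and no other deviation.

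| Per-protocol analysis | Protocol 10.1, 10.6.2.1, 10.6.2.2 | SAP 5.6 |
|---|---|---|
| CS7DA4S, Week 4 | out (no Week 4 score) | out |
| CS7DA4S, Week 24 | in | out |
| SNOT-22 at a visit with data | in | out |
| MRI (Zinreich), Week 24 | in | out |

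On this condition the two documents agree for the Week 4 endpoint and differ for the others. The protocol column treats the missing Week 4 score as a data condition; the wording on major violations is taken up under the objection.

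**2. How often could it happen?** The documents give no diary completion rate, so daily completion q is an assumption, with days taken as independent. The chance of failing the 5-of-7 rule is

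m = sum over k = 0 to 4 of C(7,k) q^k (1-q)^(7-k).

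The expected loss per arm is 21m, with 21 evaluable per arm from protocol 10.7. If the loss is equal across arms and the SD unchanged, the standard error is multiplied by 1/sqrt(1-m).

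| q | m | lost of 21 per arm | SE multiplier |
|---|---|---|---|
| 95% | 0.4% | 0.1 | 1.002 |
| 90% | 2.6% | 0.5 | 1.013 |
| 85% | 7.4% | 1.5 | 1.039 |
| 80% | 14.8% | 3.1 | 1.083 |

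For the MRI odds ratio the multiplier is approximate and assumes unchanged response proportions.

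Two cautions apply. First, only subjects who have later data and meet every other criterion are lost because of this rule. Some subjects without a Week 4 score will have left early and drop out under either definition, so for a given m the table overstates the loss. Second, missed days may cluster. If 95% completion arose because 5% of subjects recorded nothing that week, m would be 5% and not 0.4%, which is still within the range shown.

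**3. Power, as an illustration.** Protocol 10.7 gives a difference of 3.00 - 1.30 = 1.70, SD 2.4, 21 per arm and one-sided alpha 0.05, with a stated power of 73%. For one dose against sham the noncentrality is 1.70 / (2.4 x sqrt(2/21)) = 2.295. The noncentral t with 40 df gives 73.0%, which reproduces the stated figure. With 20, 19 and 18 per arm the same calculation gives 71.1%, 69.0% and 66.9%. Applying these to a later endpoint assumes that the Week 4 effect and SD hold there, which the documents do not state.

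**The case against.** The best defence is that the protocol leaves room for this choice. Protocol 10.1 also says: "Major protocol deviations and the definition of the PP analysis set will be identified and finalized based on blinded review of the data". Protocol 11.6 adds: "Major protocol violations are defined as those that could impact the performance evaluation such as a subject is ineligible, missing key data". The SAP names its exclusions in advance and finalises them blind, and a missing primary variable can fairly be called missing key data. A single fixed set also has merit. The 16-week exposure rule and the ban on certain rescue medication before Week 4 likewise apply to all endpoints, and one base population makes results comparable across them. Protocol 10.6.2.1 can be read as adding data availability on top of membership, without forbidding a further membership condition.

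Part of this stands. The sponsor may refine the set, and a fixed cohort is coherent. But the delegation sits in the same paragraph as the explicit statement that the data needed are those for the assessment being analysed, and does not cancel it. A Week 4 diary score is key data for the Week 4 analysis; it is not key data for an MRI reading at Week 24. A refinement that narrows the set belongs in SAP 3.3.

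A reader might also infer that SAP 5.6 contradicts itself, because its opening sentence accepts any assessment listed in SAP 5.5. It does not. That sentence also requires freedom from major deviations, and the list then sets out the deviations and other exclusion reasons. The conditions are cumulative; the Week 4 rule narrows the opening condition.

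**Conclusion.** The departure is real, undeclared and modest. SAP 5.6 removes from the later and MRI per-protocol results some subjects whom protocol 10.1 would keep. Under the assumed completion rates the loss runs from near 0 to about 3 of 21 per arm, with a standard error 0% to 8% larger. The lower end is as compatible with the documents as the upper, since neither document gives a rate.

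Two stronger readings are tempting. One is that the efficacy conclusions are at risk. The documents do not support it: ITT is the primary efficacy set, its analyses keep every subject at issue who has data for the endpoint, the per-protocol results are supportive, and SAP 7.8 treats all p-values as nominal. The other is that the per-protocol comparison is biased. That would require Week 4 diary lapses to differ by arm in a way related to outcome, and nothing in the documents indicates this. Requiring endpoint-specific data also conditions on information gathered after randomization, so the fix below restores evaluable subjects but does not remove that general limitation.

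**What to change.** In SAP 5.6, apply the non-missing Week 4 change only to the per-protocol analysis of the Week 4 endpoint. For every other endpoint, require non-missing data for the endpoint analysed, as protocol 10.1 states. Leave the other exclusion criteria as they are. Make the change before the analysis sets are authorised ahead of the interim database lock (SAP 5.1).

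The cost is one reworded sentence, an endpoint-level data flag, and a per-protocol N that varies by endpoint and should be shown in each table. If the sponsor prefers one fixed set, SAP 3.3 should list that departure with its reason. That would settle the documentation but would not bring the evaluable subjects back.
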